## Treatment

The visible fluorescent injectate (VFI) agent is comprised of a mixture of two different molecular weight carboxymethyl dextran molecules (5 kD and 150 kD) with different fluorescent dye molecules attached. The 5 kD carboxymethyl dextran, (FD001), is labeled with 5-aminofluorescein and the 150 kD carboxymethyl dextran, (FD003), is labeled with 2-sulfohexamine rhodamine. These fluorescent labels are covalently attached to the dextran through the carboxymethyl moiety. Please see the chemical structures for FD001 and FD003, which are shown in Figure 1 and Figure 2, respectively.

The high molecular weight labeled carboxymethyl dextran is not rapidly cleared from the vasculature and is not rapidly cleared by passive filtration in the kidneys; therefore, its concentration in the blood stream after injection provides a direct measurement of the total blood volume. The low molecular weight labeled carboxymethyl dextran is also not patient to rapid metabolism but is freely filtered by the kidneys.

The VFI is administered intravenously through a bolus injection. The anticipated single dose for a 70 kg human will consist of 35 mg of FD001 and 12 mg of FD003 diluted at 15.67 mg/mL mg/mL for a total injection of 3 mL of VFI.

There is no placebo/reference medication for this study as this is a one-armed study

[figure not shown]

Figure 1: Structure of FD001 (5 kD carboxymethyl dextran with covalently bound 5 aminofluorescein)

[figure not shown]

Figure 2: Structure of FD003 (150 kD carboxymethyl dextran with covalently bound 2 sulfohexamine rhodamine)

## Randomization

Not applicable since this is a one-armed study.

## Blinding and Unblinding

Data from the FAST PV and mGFR Technology will not be evaluable by the treating physician,

but will be made available to an adjudication committee for consideration after patient enrollment has concluded or at predetermined intervals during the course of the study.

### Sample size

The primary objective is to assess the safety and function of the FAST PV and mGFR Technology in hospitalized patients with heart failure. This is a phase II trial. It is planned to enroll 50 eligible patients. No formal hypothesis test is performed to assess the primary objective. This is justified as follows:

1. Both function and safety cannot be uniquely assessed by one specific endpoint, but there exist several relevant endpoints and endpoint-related criteria which must be investigated in order to assess the global function and safety.
2. For reasons of feasibility, the studies sample size is limited to 50 patients which is an adequate number in the context of a phase II trial. However, this limited number does not allow to address a complex multiple testing problem with adequate power.

Therefore, all analyses are purely descriptive.

### Inclusion criteria

- Written informed consent indicating that they understand the purpose of and procedures required for the study and are willing to participate in the study prior to any study related measures present
  - Hospitalized patient with acute decompensated heart failure, diagnosed on the basis of the presence of at least one symptom (dyspnea, orthopnea, or edema) and one sign (rales, peripheral edema, ascites, or pulmonary vascular congestion on chest radiography) of heart failure.
  - Subject:  $\geq 18$ . Male with female partners of childbearing potential gave agreement to practice abstinence or use condoms from enrollment through 90 days after administration of the last dose of study drug present.
- A female subject is eligible to enter the study if she is:
  - Not pregnant or nursing
  - Of non-childbearing potential (i.e., post-menopausal defined as having been amenorrheic for at least 1 year prior to screening, or has had bilateral tubal ligation at least 6 months prior to administration of study drug or bilateral oophorectomy or complete hysterectomy)
  - If of childbearing potential, must have a negative urine or serum pregnancy test prior to drug administration and be using a highly effective means of contraception during study participation and until 1 month after the last dose of study drug. Highly effective contraception methods include:
    - Total abstinence (when this is in line with the preferred and usual lifestyle of the subject. Periodic abstinence (e.g., calendar, ovulation, symptothermal, post-ovulation methods) and withdrawal are not acceptable methods

- of contraception
- Combination of any two of the following (i+ii or i+iii, or ii+iii):
  - (i) use of oral, injected or implanted hormonal methods of contraception or other forms of hormonal contraception that have comparable efficacy (failure rate < 1%), for example hormone vaginal ring or transdermal hormone contraception.
  - (ii) placement of an intrauterine device (IUD) or intrauterine system (IUS)
  - (iii) barrier methods of contraception: condom or occlusive cap (diaphragm or cervical/vault caps)
- In case of use of oral contraception women should have been stable on the same pill for a minimum of 3 months before taking study treatment
- Partner of a male patient: Agreement to use a medically acceptable method of contraception (a barrier method, intrauterine device, or hormonal contraception) from enrollment through 90 days after administration of the last dose of study drug present.
- Male patient agreed to not donate sperm from enrollment through 90 days after administration of the last dose of study drug present
- Patient is able to communicate effectively with the study personnel.
- Patient is informed of the nature and risks of the study and give written informed consent prior to enrollment.

### Exclusion criteria

- New or ongoing myocardial infarction or instable angina present at the time of planned study inclusion.
- Patient shows evidence of severe infection other than pneumonia, or active internal bleeding (characterized by recent decrease of blood hemoglobin concentration by more than 2 g/dl).
- Patient experiences new onset atrial fibrillation.
- Patient has an elective surgery planned during the 30 days they are enrolled in the study.
- Patient has a psychiatric disease or a history of illicit drug use that would prohibit them from complying with study requirements
- Prior exposure to VFI present.
- History of any clinically significant allergic or negative reactions, side effects, or anaphylaxis to fluorescent dyes, or dextran molecules present.
- Patient requires intravenous vasodilators or inotropic agents (other than digoxin or digitoxin) for heart failure.
- Patient undergoes chronic dialysis (for example peritoneal or hemodialysis) treatments.
- Patient is in cardiogenic shock or on vasopressors.
- Hypotension as defined by blood pressure < 90 systolic and/or < 50 mm Hg diastolic exists.
- Patients suffering from significant non-cardiac diseases of other organ systems (e. g. Malignancies, significant neurological diseases).
- Patient does not have a working telephone.

- 
- Patient is a pregnant or nursing (lactating) women, where pregnancy is defined as the state of a female after conception and until the termination of gestation, confirmed by a positive human chorionic gonadotropin laboratory test.
  - Lack of willingness to storage and disclosure of pseudonymous disease data in the context of the clinical trial present.
  - Subject has a participation in another interventional clinical trial during this study or within 30 days (or longer) before entry into this trial (as a minimum; 5 x elimination half-life / terminal elimination of an investigational medicinal product).
  - Subject is legally detained in an official institution.
  - Subject is dependent on the sponsor, the investigator or the trial sites.

## **2 Analysis sets**

### **2.1 Definitions**

The full analysis set (FAS) comprises all subjects who received at least one dose of VFI. The FAS will be based on the intention-to-treat principle.

The per-protocol population (PPP) will include all subjects in the FAS without major protocol violations. Prior to the analysis, the protocol violations will be evaluated and for each patient a decision regarding the allocation to the analysis populations will be made during the data review meeting (see section 6).

There will be no separate safety analysis set since there are only two dosing visits within two days.

### **2.2 Application**

All analyses including safety evaluations will be done in the FAS. For the efficacy endpoints the analysis will also be done in the PPP as a sensitivity analysis.

## **3 Trial centres**

50 patients with acute decompensated heart failure were enrolled at the Nephrology and Cardiology departments of Charité - Universitätsmedizin Berlin as well as at the Kerckhoff-Klinik Bad Nauheim.

## **4 Analysis variables**

### **4.1 Demography and baseline characteristics**

- Age at inclusion (years)
- Gender
- Ethnicity
- Height (cm)
- Weight (kg)

- 
- BMI (kg/m^2)
  - Paroxysmal nocturnal dyspnea during previous 3 days
  - Night cough
  - Cardiomegaly (clinical or on chest X-ray or echocardiography)
  - S3 gallop
  - Hepatojugular reflux
  - Hepatomegaly
  - Pleural effusion
  - Last stable body weight before admission ("best body weight")(kg)
  - NYHA-Stage
  - Systolic Blood Pressure
  - Diastolic Blood Pressure
  - Mean Arterial Pressure
  - SpO2
  - Heart rate
  - Respiratory rate
  - Comorbidities (Chronic Kidney Disease stage, previous myocardial infarction, hypertension, preexisting coronary heart disease, preexisting congestive heart failure, previous hospitalization for acute decompensated heart failure, Diabetes mellitus, Cerebral vascular disease, Peripheral arterial occlusive disease, Other comorbidities)
  - Medication on admission (ACE inhibitor, AT1 receptor blocker, AT1/Neprilysin inhibitor, Loop diuretic, Furosemide p.o. including dosage (mg) per 24h prior to dosing, Torasemide p.o. including dosage (mg) per 24h prior to dosing, Thiazide diuretic, Aldosterone antagonist, beta-Blocker, Nitrates, Digoxin/Digitoxin)
  - Structural Heart disease Criteria (Last documented left ventricular ejection fraction (%), evidence of left ventricular hypertrophy, evidence of left atrial enlargement, evidence of diastolic dysfunction, other cause of heart failure)
  - Baseline Serum creatinine and Baseline eGFR
  - eGFR Day1
  - Serum creatinine Day 1
  - NT-proBNP
  - Hematocrit
  - Serum Sodium from routine lab

#### 4.2 Primary variables

Global aim is to assess the safety and function of the FAST PV and mGFR Technology in hospitalized patients with heart failure.

- Absolute and relative frequencies of AEs and SAEs related to VFI.
- Plasma stability of the FD003 high molecular weight marker over the 15, 30, and 60 minute blood draws at day 1 and 3

### 4.3 Secondary variables

#### 4.3.1 Efficacy

- Estimated PV (by Kaplan-Hakim's formula, see chapter 7.2) and measured PV (assessed by FAST methodology) on days 1 and 3
- Estimated TBV (by Nadler's formula, see chapter 7.2) and measured TBV (mTBV: calculated from mPV and measured hematocrit, see chapter 7.2) on days 1 and 3
- Estimated GFR (CKD-EPI formula, sMDRD, Cystatin C formula, and Creatinine-Cystatin C formula, see chapter 7.2) and measured GFR (assessed by FAST methodology) on days 1 and 3 in heart failure patients undergoing active fluid management
- Development of AKI within 72 hours after day 1 and 48 hours after day 3 respectively
- Current level and level within last 24 hours of well-being, dyspnea, dizziness, nausea reported on day 1 and day 3
- Subjectively reported symptoms (PGA, dyspnea, dizziness, nausea) determined using patient symptom assessment sheets within the following 24 and 48 hours on day 1 and following 24 and 48 hours on day 3
- Low-output complications within the next 24 and 48 hours (e. g. subjectively reported dizziness/nausea, PGA, hypotension (Systolic <100, diastolic <60mmHg), need for iv-fluid therapy) at day 1 and within the next 24 and 48 hours at day 3
- Risk of being refractory to diuretic therapy (e. g. require dosage increases of furosemide/torsemide, require ultrafiltration/RRT within the next 24-48 hours, fail to improve subjectively in PGA and dyspnea scales) within 24 and 48 hours on day 1 and day 3

#### 4.3.2 Safety/Tolerability

- Length of stay, dialysis/ultrafiltration requirement, or rehospitalization within 30 days, or mortality
- Laboratory values (Serum creatinine (mg/dl), Hematocrit (%), creatine phosphokinase (CPK) (U/l), NT-proBNP (ng/l), Alanine aminotransferase (ALT) (U/l), Aspartate aminotransferase (AST) (U/l), Alkaline phosphatase (AP) (U/l), bilirubin, total and direct (mg/dl), INR (dimensionless)) collected on day 1, 3, 5 (except for serum creatinine which is collected on all days and hematocrit which is only collected on day 1)
- Occurrence of AEs and SAEs
- Routine clinical parameters (Serum creatinine on admission (mg/dl), Baseline serum creatinine (nadir from inspection of previous, lab values or by primary care physician) (mg/dl), Serum creatinine (mg/dl), Serum sodium (mmol/l), Serum potassium (mmol/l), eGFR (CKD-EPI) (ml/min/1.73 m^2), Hemoglobin (g/dl), Serum-Albumin (g/dl), Urine output (0:00 - 24:00 on the indicated day) (ml/24 h) (if, incomplete, extrapolate the available time period to 24 hours), Chest X-ray: evidence of pulmonary congestion, Chest X-ray: evidence of pleural effusion, Chest X-ray: evidence of cardiomegaly, Alanine aminotransferase (ALT) (U/l), Aspartate aminotransferase (AST) (U/l), Alkaline phosphatase (AP) (U/l), Bilirubin, total and direct (mg/dl))

## **5 Handling of missing values and outliers**

### **5.1 Missing values**

For the safety assessment of the AEs and SAEs, completeness of the data (severity, relationship, and seriousness) is required. The rate of missing values for the concentrations of FD003 is expected to be low. A decision on how to handle missing value for these values will be made during the data review (see section 6). Serum creatinine values missing at day 1 or 3 will be replaced by the respective values of day 0 and day 4 or the routine measurements at these days, if the aforementioned values are not available. For secondary parameters, missing values will not be replaced.

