**Table 6: Clinical presentation/Exam Parameters**

\*Height (cm)

Weight (kg)

\*Paroxysmal nocturnal dyspnea during previous 3 days?

\*Night cough

\*Cardiomegaly (clinical or on chest X-ray or echocardiography)

\*S3 gallop

\*Hepatojugular reflux

\*Hepatomegaly

\*Pleural effusion

\*Last stable body weight before admission ("best body weight")(kg)

NYHA stage (0-4)

Ankle/lower extremity edema (grade 0-4; according to Guelph General Hospital Congestive Heart Failure Pathway)

Pulmonary rales

Systolic blood pressure (mmHg) (morning, supine)

Diastolic blood pressure (mmHg) (morning, supine)

\*\*Systolic blood pressure (mmHg) (morning, 30 sec after standing up)

\*\*Diastolic blood pressure (mmHg) (morning, 30 sec after standing up)

Heart rate (beats per minute)(morning, supine)

Heart rate (beats per minute)(morning, 30 sec after standing up)

SpO2 (%) (morning)

Jugular venous distension (>4 cm above sternal angle with 45° upper body elevation ) (morning)

Respiratory rate (breaths per minute) (morning)

O2 supply requirement (in L/min) (morning)

\*Only assessed Day 1

\*Only assessed Day 1 and Day 3

Table 7: Study-related laboratory measurements
Serum creatinine (mg/dl)
*Hematocrit (%)
** creatine phosphokinase (CPK) (U/l)
**NT-proBNP (ng/l)
**Alanine aminotransferase (ALT) (U/l)
**Aspartate aminotransferase (AST) (U/l)
**Alkaline phosphatase (AP) (U/l)
**bilirubin, total and direct (mg/dl)
**INR (dimensionless)
Storage of EDTA Plasma, Heparin-Plasma, Serum, whole blood, centrifuged urine (10 aliquots a 200 µl each) at ≤ -75°C

\*Only Collected Day 1 and Day 3; For use in calculating an ePV from Nadler's formula

\*\* Only Collected Day 1, 3 and 5

Table 8: Routine clinical parameters
*Serum creatinine on admission (mg/dl)
*Baseline serum creatinine (nadir from inspection of previous lab values or by primary care physician) (mg/dl)
Serum creatinine (mg/dl)
Serum sodium (mmol/l)
Serum potassium (mmol/l)
eGFR (CKD-EPI) (ml/min/1,73 m  )
Hemoglobin (g/dl)
Serum-Albumin (g/dl)
Urine output (0:00 - 24:00 on the indicated day) (ml/24 h) (if incomplete, extrapolate the available time period to 24 hours)
Chest X-ray: evidence of pulmonary congestion
Chest X-ray: evidence of pleural effusion
Chest X-ray: evidence of cardiomegaly
Alanine aminotransferase (ALT) (U/l)
Aspartate aminotransferase (AST) (U/l)
Alkaline phosphatase (AP) (U/l)
Bilirubin, total and direct (mg/dl)
INR (dimensionless)

\*Only on Day 1

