To evaluate whether eGFR calculation by the CKD-EPI formula and sMDRD formula on days 1 and 3 provides an accurate estimate of measured GFR (mGFR; assessed by FAST methodology) in heart failure patients undergoing active fluid management, linear regression models with the measured value at a given day as dependent variable and the estimated version as independent variable will be generated. The models will be adjusted for mPV and mPVS. Further, Bland-Altman plots will be generated comparing the estimated and measured parameters separately for day 1 and day 3. The defined limits of agreements are  $\pm 6\text{ml/min}$ . Diagnostic accuracy including frequencies of values between 15% and 30% of the measured value will be determined as mentioned before.

To evaluate whether patients with a low mGFR/eGFR ratio on days 1 and 3 are at higher risk of developing AKI within the following 72 (day 1) and 48 (day 3) hours, logistic regression models with the AKI status as dependent variable and mGFR/eGFR ratio as independent variables will be generated. The models will be adjusted for mPVS, mTBVS. Three different versions of the mGFR/eGRF ratio will be evaluated: ratio  $< 1$ ; ratio  $<$  first quartile; ratio as continuous parameter.

To evaluate whether ranges of mPVS (low mPVS ( $< -10\%$ ), normal mPVS ( $-10$  to  $+10\%$ ), high mPVS ( $> +10\%$ )) and/or mTBVS (low mTBVS ( $< -10\%$ ), normal mTBVS ( $-10$  to  $+10\%$ ), high mTBVS ( $> +10\%$ )) on days 1 and 3 are associated with subjectively reported symptoms (current PGA  $> 15$ , current dyspnea  $> 15$ , current dizziness  $> 15$ , current nausea  $> 15$ ) determined using patient symptom assessment sheets within the following 24-48 hours, a logistic regression

---

model with occurrence of symptoms (PGA, dyspnea, dizziness, nausea) as dependent variable and the categorized measured value (mPVS, mTBVS) as independent variables will be generated. The models will be adjusted for mean arterial pressure.

To evaluate whether patients with low mPVS ( $< -10\%$ ) or low mTBVS ( $< -10\%$ ) on day 1 or on day 3 are at risk of developing low-output complications within the next 24-48 hours (subjectively reported dizziness  $> 15$ , nausea  $> 15$ , PGA  $< 25$ , hypotension (Systolic  $< 100$ , diastolic  $< 60$  mmHg), need for iv-fluid therapy), logistic regression models using mPVS and mTBVS as independent variables will be used.

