To evaluate whether patients with a high mPVS ( $> +10\%$ ) or a high mTBVS ( $> +10\%$ ) on day 1 and/or day 3 are at risk of being refractory to diuretic therapy (defined as any dosage increases of furosemide i.v. dose equivalent, adding thiazide after day 1, require ultrafiltration/RRT within the next 24-48 hours, fail to improve subjectively in PGA and dyspnea scales, fail of mean weight loss during the study period Day 1-Day 5 of at least 0,5 kg/d) logistic regression models using mPV and mTBV as independent variables will be used.

To evaluate whether the changes of ePV (using relative and absolute change as well as the Strauss' formula) and eTBV (using relative and absolute change) from day 1 to day 3 adequately reflects the changes of mPV and mTBV Bland-Altman plots will be generated. These plots will be analysed exploratory, since no appropriate values for limits of agreements are available. The amount of values within 10% and within 30% of the measured values will also be determined. In addition, the diagnostic test accuracy including 95% confidence interval as proposed by Obuchowski will be calculated.

To evaluate whether the change of mPV and mTBV and changes of mPVS and mTBVS from day 1 to day 3 as well as the mPVS and mTBVS on Day 1 and Day 3 is predictive of the remaining length of stay at the given day (i.e. remaining length of stay starting with day 1 or with day 3), dialysis/ultrafiltration requirement, or rehospitalization within 30 days, or mortality, linear (remaining length of stay), logistic (dialysis/ultrafiltration, rehospitalization within 30 days) or Cox-regression models (mortality) will be utilized using changes of mPV and mTBV from day 1 to day 3 (first model), changes of mPVS and mTBVS from day 1 to day 3 (second model), and mPVS and mTBVS at day 1 (third model) and day 3 (fourth model) as independent variables.

To evaluate whether the percentage changes of mGFR from day 1 to day 3 ( $< 0$  vs.  $\geq 0$ ; continuous) predicts the percentage changes of eGFR from day 2 to day 4 (CKD-EPI formula only;  $< 0$  vs.  $\geq 0$ ; continuous), a logistic as well as a linear regression model will be used.

The same will be done to investigate the changes in eGFR from day 1 to day 3 (all formulas) as the dependent variable. Further, exploratory Bland-Altman plots without predefined limits of agreement will be created.

To evaluate whether patients with a high PVS or TBVS on Day 1 ( $> +10\%$ ) and a decreasing PVS

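### SAP 5.1 fills a missing Day 3 creatinine from Day 4, so data from the AKI outcome window enter the Day 3 predictor and break the same-day comparison with mGFR

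*SAP*

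**What the plan says.** - **Replacement rule (SAP 5.1).** "Serum creatinine values missing at day 1 or 3 will be replaced by the respective values of day 0 and day 4", continuing "or the routine measurements at these days, if the aforementioned values are not available". The phrase about these days could mean Days 1 and 3 or Days 0 and 4.
- **Next rule in the same section.** "For secondary parameters, missing values will not be replaced". SAP 4.3.1 lists estimated GFR and AKI among the secondary variables.
- **Outcome (SAP 4.3.1).** "Development of AKI within 72 hours after day 1 and 48 hours after day 3 respectively".
- **AKI model (SAP 7.7.1).** "logistic regression models with the AKI status as dependent variable and mGFR/eGFR ratio as independent variables will be generated". The ratio is used in three forms: below 1, below the first quartile, and "ratio as continuous parameter".
- **Other uses of Day 3 eGFR (SAP 7.7.1).** It is compared with Day 3 mGFR by regression, by Bland-Altman plot with limits of ±6 mL/min, and by the share of values within 15% and 30%. A further analysis takes "changes in eGFR from day 1 to day 3 (all formulas) as the dependent variable".
- **Data collected.** Table 1 schedules study-related laboratory tests on Days 1 to 5, and routine clinical parameters (which include creatinine) on the same days plus a retrospective pre-dose entry. Table 8 of the protocol also records an admission creatinine and a nadir baseline creatinine. Neither document gives an AKI threshold or says which creatinine is the reference.

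**The concern.** A predictor measured at a landmark should use only what was known at that landmark. Here Day 3 is the landmark and AKI in the following 48 hours is the outcome. Filling Day 3 from Day 4 gives the predictor part of the outcome's own course. If creatinine is rising, the filled eGFR is too low and the ratio too high, so a patient heading towards AKI looks less like a low-ratio patient. That works against the hypothesis under study.

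The same fill disturbs two analyses that do not depend on AKI. The agreement analysis assumes that mGFR and eGFR belong to the same day, in patients whose renal function may be changing under active fluid management. The Day 1-to-3 eGFR change would span a different interval in filled patients.

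The rule also looks backward for Day 1 and forward for Day 3, and the SAP gives no reason for the difference.

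**Working it through.** The plan gives no figure of its own to reproduce here, so the check uses the CKD-EPI creatinine formula in SAP 7.2.

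**Step 1: timing.** The second AKI window covers the 48 hours after Day 3. Day 4 lies within it. Day 0, used for a missing Day 1 value, lies before the first window, so the Day 1 fill does not look ahead.

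**Step 2: order of sources.** If the ambiguous phrase means Days 1 and 3, a same-day routine creatinine is used only when the Day 4 value is absent. If it means Days 0 and 4, a same-day routine value is never used.

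**Step 3: effect on the ratio.** Above kappa, eGFR is proportional to creatinine^-1.209, and the age and sex terms cancel within a patient. Hence

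filled ratio = true ratio × (Day 4 creatinine / Day 3 creatinine)^1.209.

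The multiplier is 1.12, 1.25, 1.31 and 1.63 for rises of 10%, 20%, 25% and 50%.

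Example with assumed values: man aged 75, formula without the race coefficient, true Day 3 creatinine 1.5 mg/dL, eGFR 44.9, mGFR set at 0.8 × 44.9.

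| Day 4 creatinine (mg/dL) | Day 3 eGFR after fill | Error in eGFR | Ratio after fill (true 0.80) |
|---|---|---|---|
| 1.3 | 53.4 | +8.5 | 0.67 |
| 1.5 | 44.9 | 0 | 0.80 |
| 1.65 | 40.0 | -4.9 | 0.90 |
| 1.8 | 36.0 | -8.9 | 1.00 |
| 2.0 | 31.7 | -13.2 | 1.13 |
| 2.25 | 27.5 | -17.4 | 1.31 |

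A true ratio r reaches the cut-off of 1 when creatinine rises by the factor (1/r)^(1/1.209). That is a rise of about 9%, 20% and 34% for r = 0.9, 0.8 and 0.7.

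**Step 4: agreement analysis.** In the table, a 20% rise (1.5 to 1.8) shifts eGFR by 8.9, and the fall to 1.3 shifts it by 8.5. Both exceed the ±6 mL/min limits. A larger assumed change, 1.2 to 1.6 mg/dL in a man aged 72, takes eGFR from 60.05 to 42.41. That is a shift of 17.6, or 29%, close to the edge of the 30% band. The sMDRD and creatinine-cystatin C formulas shift in the same direction; the cystatin C formula does not use creatinine and is unaffected.

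**Step 5: AKI outcome.** Take an assumed threshold of a 0.3 mg/dL rise and an assumed nadir of 1.2 mg/dL.
- Path 1.5, 1.8, 1.9 on Days 3, 4, 5, judged from Day 3: the true rise is 1.9 - 1.5 = 0.4. After the fill it is 1.9 - 1.8 = 0.1, and the event is missed.
- Path 1.5, 1.5, 1.9, judged from Day 3: the rise is 0.4 with or without the fill.
- Either path judged against the nadir: 1.9/1.2 = 1.58 with or without the fill.

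**Step 6: possible effect on the model.** This simulation is illustrative, with every parameter assumed: true slope -3 on the log ratio, AKI in about 16%, every AKI rise complete by Day 4, and values missing at random. With the outcome kept correct and only the predictor filled, the fitted slope was -2.98, -2.55, -2.08 and -1.34 at 0%, 5%, 10% and 20% missing. Because every rise falls on Day 4, this is an unfavourable case. The documents give no missing rate; 2% to 20% of the planned 50 patients would be 1 to 10 patients.

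**The case against.** **The rule affects few patients.** This stands. A Day 3 ratio needs a Day 3 mGFR, and so a second dose and its timed draws. A patient who misses Day 3 altogether has no ratio to distort. The fill matters only for someone dosed and sampled on Day 3 who has no study creatinine that day, although one is scheduled daily.

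**The bias has no fixed direction.** This also stands. The fill applies to anyone with the value missing, not only to patients who are deteriorating. A fall in creatinine reverses the error, and a stable value produces none.

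**A same-day routine value may not exist.** This stands in part. The protocol synopsis enters routine values as available and mandates no routine draw. That limits how often the better source can be used, but does not justify ranking it behind a later value.

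**Data review could catch the problem.** SAP 5.2 plots each patient's creatinine series, and SAP 6 allows documented changes before analysis. Nothing there tells the meeting to set this rule aside, so the written rule would apply by default.

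**A stronger reading is tempting: that the rule hides AKI.** The documents do not support it as a general statement. Masking needs AKI to be judged as a rise from Day 3 and the rise to occur by Day 4. A rise from Day 4 to Day 5 stays visible, and AKI judged against the recorded nadir is untouched. The documents do not say which reference applies.

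**Conclusion.** The concern holds in a limited form. As written, SAP 5.1 puts a value from the outcome window into the Day 3 predictor and breaks the same-day pairing of eGFR and mGFR. It also lengthens the interval of the Day 1-to-3 eGFR change. These effects do not depend on how AKI is defined. For an affected patient the error can be material: a 25% higher ratio for a 20% one-day rise, and an eGFR shift larger than the SAP's own agreement limits.

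Across the trial the effect is probably modest but cannot be sized, because the number of missing values is not given. The analyses concerned are secondary, and the SAP calls all its analyses descriptive. The primary safety and FD003 stability results are not touched. The creatinine paths, ages, AKI threshold, nadir, missing rates and simulation settings above are assumptions; the exponent, the window, the limits and the order of sources come from the SAP. The order of sources rests on the natural reading of an ambiguous sentence, but the Day 4 fill is explicit.

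**What to change.** Rewrite the creatinine sentence in SAP 5.1 as follows:
- Use a routine creatinine from the same day first, where one is recorded.
- If there is none, leave the value missing in the main analysis.
- Use an earlier value only in a sensitivity analysis. It is not neutral either: carrying Day 2 forward in a patient whose creatinine is rising understates Day 3 creatinine, lowers the ratio and enlarges the apparent rise.
- Never use a later value.

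In the same edit, name the source meant by day 0 (study-related sampling starts on Day 1, so presumably a retrospective routine value). Reconcile the rule with the statement that secondary parameters are not replaced. Report how many values were filled and from which source. State the reference creatinine for AKI in SAP 4.3.1, so that a reader can tell whether the outcome is affected.

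The cost is a few sentences and no new data collection. The downside is that a few patients without any same-day creatinine may drop out of the Day 3 models.
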